### **10.3.2 Day 1/Week 0 procedures (Quarterly visit schedule)**

After a patient (or parent or guardian) has provided informed consent, met all inclusion and none of the exclusion criteria, the following assessments are to be completed at Day 1/Week 0 as follows:

- Complete physical exam: within 24 hours prior to olipudase alfa infusion (pre-infusion).
- Neurological exam: within 24 hours prior to olipudase alfa infusion (pre-infusion).
- Body weight, height, BMI: within 24 hours prior to olipudase alfa infusion (pre-infusion).
- Vital signs: Before (within 30 minutes prior) infusion, halfway through infusion, and after infusion ( $\pm 10$  minutes). Postinfusion vital signs are measured every 30 minutes for the first 2 hours, hourly for 2 to 6 hours postinfusion, and then once every 8 hours until the patient is discharged ( $\pm 10$  minutes).

- ECG: in triplicate within 24 hours prior to olipudase alfa infusion (pre-infusion); in single analysis at the end of infusion (within 10 minutes following end of infusion), 24 and 48 hours following end of infusion ( $\pm 3$  hours).
- Clinical laboratory samples for liver function testing, clinical chemistry, hematology, and coagulation: as indicated by age cohort in [Section 1.3](#) and [Section 1.4](#). Preinfusion samples to be collected within 24 hours prior to olipudase alfa infusion. Post infusion samples to be collected  $\pm 3$  hours from scheduled time.
  - Urinalysis: within 24 hours prior to olipudase alfa infusion (pre-infusion).
- Urine  $\beta$ -hCG pregnancy test: within 24 hours prior to olipudase alfa infusion (pre-infusion).
- Safety biomarkers: as indicated by age cohort in [Section 1.3](#) and [Section 1.4](#). Preinfusion samples to be collected within 24 hours prior to olipudase alfa infusion. Post infusion samples to be collected  $\pm 3$  hours from scheduled time.
- Immunogenicity samples: within 24 hours prior to olipudase alfa infusion (pre-infusion).
- Efficacy biomarkers: within 24 hours prior to olipudase alfa infusion (pre-infusion).
- Lipid profile: as indicated by age cohort in [Section 1.2](#). Preinfusion samples to be collected within 24 hours prior to olipudase alfa infusion.
- Bone biomarkers: as indicated by age cohort in [Section 1.2](#), within 24 hours prior to olipudase alfa infusion (pre-infusion).
- Plasma and/or DBS sphingomyelin and metabolites: as indicated by age cohort in [Section 1.3](#) and [Section 1.4](#). Preinfusion samples to be collected within 24 hours prior to olipudase alfa infusion. Post infusion samples to be collected  $\pm 3$  hours from scheduled time.

#### **10.3.3 Dose escalation visits and 2nd infusion at 3.0 mg/kg or highest tolerated dose procedures**

The following assessments are to be completed for each dose escalation visit:

- Abbreviated physical exam: within 24 hours prior to olipudase alfa infusion (pre-infusion).
- Doppler echocardiogram: within 24 hours prior to the first infusion of 3.0 mg/kg olipudase alfa or highest tolerated dose (pre-infusion).
- Body weight, height, BMI: within 24 hours prior to olipudase alfa infusion (pre-infusion).
- ECG: with each new dose  $\geq 0.3$  mg/kg; within 24 hours prior to olipudase alfa infusion (pre-infusion), at the end of infusion (within 10 minutes following end of infusion), 24 hours and 48 hours following end of infusion ( $\pm 3$  hours).
- Vital signs: Every visit. Before (within 30 minutes prior) infusion, halfway through infusion, and after infusion ( $\pm 10$  minutes). Postinfusion vital signs are measured every 30 minutes for the first 2 hours, hourly for 2 to 6 hours postinfusion, and then once every 8 hours until the patient is discharged ( $\pm 10$  minutes).

- Liver function testing: as indicated by age cohort in [Section 1.3](#) and [Section 1.4](#). Preinfusion samples to be collected within 24 hours prior to olipudase alfa infusion. Post infusion samples to be collected  $\pm 3$  hours from scheduled time.
- Urine  $\beta$ -hCG pregnancy test: within 24 hours prior to olipudase alfa infusion (pre-infusion, every 4 weeks).
- Safety biomarkers: as indicated by age cohort in [Section 1.3](#) and [Section 1.4](#). Preinfusion samples to be collected within 24 hours prior to olipudase alfa infusion. Post infusion samples to be collected  $\pm 3$  hours from scheduled time.
- Plasma and/or DBS sphingomyelin and metabolites: as indicated by age cohort in [Section 1.3](#) and [Section 1.4](#). Preinfusion samples to be collected within 24 hours prior to olipudase alfa infusion. Post infusion samples to be collected  $\pm 3$  hours from scheduled time.
- Immunogenicity samples: within 24 hours prior to olipudase alfa infusion (pre-infusion) every 2 weeks from Day 1/Week 0 through Week 16.
- Pharmacokinetics: with the first infusion at 0.3, 1.0 and 3.0 mg/kg. See [Section 1.5](#) for sample collection times per age cohort.

#### **10.3.4 Quarterly visit procedures at Week 12 and Week 38**

The following assessments are to be completed for the Week 12 and Week 38 visit:

- Tanner staging: within 24 hours prior to olipudase alfa infusion (pre-infusion).
- Complete physical exam: within 24 hours prior to olipudase alfa infusion (pre-infusion).
- Neurological exam: within 24 hours prior to olipudase alfa infusion (pre-infusion).
- Body weight, height, BMI: within 24 hours prior to olipudase alfa infusion (pre-infusion).
- Vital signs: Before (within 30 minutes prior) infusion, halfway through infusion, and after infusion ( $\pm 10$  minutes). Postinfusion vital signs are measured every 30 minutes for the first 2 hours, hourly for 2 to 6 hours postinfusion, and then once every 8 hours until the patient is discharged ( $\pm 10$  minutes).
- ECG: within 24 hours prior to olipudase alfa infusion (pre-infusion), at the end of infusion (within 10 minutes following end of infusion), 24 hours and 48 hours following end of infusion ( $\pm 3$  hours).
- Clinical laboratory samples for liver function testing, clinical chemistry, hematology, and coagulation: as indicated by age cohort in [Section 1.3](#) and [Section 1.4](#). Preinfusion samples to be collected within 24 hours prior to olipudase alfa infusion. Post infusion samples to be collected  $\pm 3$  hours from scheduled time.
  - Urinalysis: within 24 hours prior to olipudase alfa infusion (pre-infusion).
- Urine  $\beta$ -hCG pregnancy test: within 24 hours prior to olipudase alfa infusion (Week 12 only, pre-infusion).

- Safety biomarkers: as indicated by age cohort in [Section 1.3](#) and [Section 1.4](#). Preinfusion samples to be collected within 24 hours prior to olipudase alfa infusion. Post infusion samples to be collected  $\pm 3$  hours from scheduled time.
- Immunogenicity samples: within 24 hours prior to olipudase alfa infusion (pre-infusion).
- Lipid profile: as indicated by age cohort in [Section 1.2](#). Preinfusion samples to be collected within 24 hours prior to olipudase alfa infusion.
- Pharmacokinetics: if applicable at Week 12 with the first infusion at 1.0 mg/kg. See [Section 1.5](#) for sample collection times per age cohort.
- Plasma and/or DBS sphingomyelin and metabolites: as indicated by age cohort in [Section 1.3](#) and [Section 1.4](#). Preinfusion samples to be collected within 24 hours prior to olipudase alfa infusion. Post infusion samples to be collected  $\pm 3$  hours from scheduled time.

#### **10.3.5 Quarterly visit procedures at Week 26 and Week 52**

The following assessments are to be completed for Week 26 and Week 52 visits:

- Tanner staging: within 24 hours prior to olipudase alfa infusion (pre-infusion).
- Complete physical exam: within 24 hours prior to olipudase alfa infusion (pre-infusion).
- Neurological exam: within 24 hours prior to olipudase alfa infusion (pre-infusion).
- Body weight, height, BMI: within 24 hours prior to olipudase alfa infusion (pre-infusion).
- Patient photos: within 24 hours prior to olipudase alfa infusion (Week 52, pre-infusion, optional).
- Doppler echocardiogram: within 24 hours prior to olipudase alfa infusion (Week 52 only, pre-infusion). Vital signs: Before (within 30 minutes prior) infusion, halfway through infusion, and after infusion ( $\pm 10$  minutes). Postinfusion vital signs are measured every 30 minutes for the first 2 hours, hourly for 2 to 6 hours postinfusion, and then once every 8 hours until the patient is discharged ( $\pm 10$  minutes).
- Vital signs: Before (within 30 minutes prior) infusion, halfway through infusion, and after infusion ( $\pm 10$  minutes). Postinfusion vital signs are measured every 30 minutes for the first 2 hours, hourly for 2 to 6 hours postinfusion, and then once every 8 hours until the patient is discharged ( $\pm 10$  minutes).
- ECG: within 24 hours prior to olipudase alfa infusion (pre-infusion), at the end of infusion (within 10 minutes following end of infusion), 24 hours and 48 hours following end of infusion ( $\pm 3$  hours).
- Clinical laboratory samples:
  - Liver function testing, clinical chemistry and coagulation: as indicated by age cohort in [Section 1.3](#) and [Section 1.4](#). Preinfusion samples to be collected within 24 hours prior to olipudase alfa infusion. Post infusion samples to be collected  $\pm 3$  hours from scheduled time.
  - Hematology

- a) Week 26: within 24 hours prior to olipudase alfa infusion (pre-infusion), 24 hours (adolescent cohort only) and 48 hours following end of infusion ( $\pm 3$  hours).
- b) Week 52:
  - Pre-infusion: Two (2) samples to be collected greater than 12 hours but less than 24 hours apart. The first sample can be collected up to 24 hours prior to olipudase alfa administration at Week 52. If necessary, the second sample may be collected following olipudase alfa infusion at Week 52.
  - 24 hours following end of infusion (adolescent cohort only,  $\pm 3$  hours).
  - 48 hours following end of infusion ( $\pm 3$  hours).
- c) Urinalysis: within 24 hours prior to olipudase alfa infusion (pre-infusion).
- Urine  $\beta$ -hCG pregnancy test: within 24 hours prior to olipudase alfa infusion (Week 52 only, pre-infusion).
- Safety biomarkers: as indicated by age cohort in [Section 1.3](#) and [Section 1.4](#). Preinfusion samples to be collected within 24 hours prior to olipudase alfa infusion. Post infusion samples to be collected  $\pm 3$  hours from scheduled time.
- Immunogenicity samples: within 24 hours prior to olipudase alfa infusion (pre-infusion).
- Spleen and liver volume by MRI: within 7 days after Week 26 or Week 52 olipudase alfa infusion.
- Pulmonary imaging by HRCT (Week 52 only): within 7 days after Week 52 olipudase alfa infusion.
- Pulmonary function testing: within 7 days after Week 26 or Week 52 olipudase alfa infusion.
- Chest X-ray (at selected sites, Week 52 only): within 7 days after Week 52 olipudase alfa infusion.
- Hand X-ray (Week 52 only): within 7 days after Week 52 olipudase alfa infusion.
- Cycle ergometry: within 7 days after Week 26 or Week 52 olipudase alfa infusion.
- Liver ultrasound Doppler: within 7 days after Week 52 olipudase alfa infusion.
- Physician global assessment: within 24 hours prior to Week 26 or Week 52 olipudase alfa infusion.
- Efficacy biomarkers: within 24 hours prior to olipudase alfa infusion (pre-infusion).
- Lipid profile: within 24 hours prior to olipudase alfa infusion (pre-infusion).
- Bone biomarkers: as indicated by age cohort in [Section 1.2](#), within 24 hours prior to olipudase alfa infusion (pre-infusion).
- Plasma and/or DBS sphingomyelin and metabolites: as indicated by age cohort in [Section 1.3](#) and [Section 1.4](#). Preinfusion samples to be collected within 24 hours prior to olipudase alfa infusion. Post infusion samples to be collected  $\pm 3$  hours from scheduled time.

- Health outcome questionnaires: within 7 days after Week 26 and Week 52 olipudase alfa infusion.
- Cognitive and adaptive function testing: within 7 days after Week 26 and Week 52 olipudase alfa infusion.
- Pharmacokinetics (Week 52 only): See [Section 1.5](#) for sample collection times per age cohort.

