#### 10.6.1.3.2.2 Acute phase reactions

Acute phase reactions observed in the phase 1 and phase 1b studies are considered as one type of IAR, specific to the infused olipudase alfa therapy (5, 6). From observations in both studies the APR reactions typically occurred within 12-72 hours following an infusion of olipudase alfa and were indicative of an inflammatory response. APRs were associated with elevations in hsCRP and changes acute phase reactants including, but not limited to, neutrophils, iron, ferritin, fibrinogen, D-dimer, transferrin, albumin, protime, and partial thromboplastin time. Patient AEs associated with the APR included (but are not limited to) pyrexia, nausea, vomiting, fatigue, and pain. Acute phase reaction is determined based on combined significant laboratory findings and clinical symptoms.

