2.8 ANALYSIS OF EXPLORATORY EFFICACY VARIABLES

All exploratory efficacy analyses to assess changes in organomegaly (spleen and liver), infiltrative lung disease, linear patient growth, pulmonary function, bone age, cycle ergometry endpoints, physician's global assessment, efficacy biomarkers, lipid profile, bone biomarkers, health outcome questionnaires, cognitive functioning and adaptive functioning will be performed using the mITT population. For each exploratory efficacy assessment, observed measures and changes from baseline, as appropriate, will be listed and summarized, including the p-value from analysis of covariance with baseline as covariate and 95% CIs as appropriate, separately by time point, age group cohorts and overall.

Baseline for exploratory efficacy variables will be defined as the last non-missing value before the first infusion.

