2.8.8 Cycle ergometry

Cycle ergometry will be performed at Screening and within 1 week after infusion at Week 26 and Week 52 (or at withdrawal if withdrawn prematurely and not done within 12 weeks prior to withdrawal). This assessment is not required in patients that are ≤ 6 years of age or < 120 cm in height on Day 1/Week 0. Completion of the assessment may depend upon patient cooperation.

Cycle ergometry assessments will include maximum workload (watts), percent predicted maximum workload (%), working time (min), maximum heart rate (breaths/min), maximum percent predicted heart rate (%), maximum O₂ saturation (%), maximum respiratory rate (breaths/min), maximum ventilation (L/min), maximum O₂ uptake (mL/min), maximum percent predicted O₂ uptake (%), maximum CO₂ output (mL/min), and maximum respiratory exchange ratio.

Assessments will be summarized at each time point along with change from baseline by age group cohorts and overall.

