2.8.13 Health outcome questionnaires

Health outcome measures were evaluated using questionnaires designed to measure general quality of life (QOL) with the Pediatric Quality of Life (PedsQL) scale, fatigue with the PedsQL Multidimensional Fatigue Scale, and pain with the PedsQL Pediatric Pain Questionnaire. These will be evaluated at Screening, Week 26 and Week 52 (or at withdrawal if withdrawn prematurely).

and not done within 12 weeks prior to withdrawal), and will be analyzed in accordance to the tool manuals.

PedsQL Generic Core Scales

The PedsQL includes a child self-report for patients age 5 to 18 years and a report for parents of patients age birth to 18 years. For patients age 5 to 18 years, the 23-item PedsQL Generic Core Scales for both patient and parent reports include four Scales, Physical Functioning (8 items), Emotional Functioning (5 items), Social Functioning (5 items), and School Functioning (5 items). For patients age 2 to 4 years, the 21-item PedsQL Generic Core Scales for the parent reports include 8 items in Physical Functioning Scale, 5 items in Emotional Functioning Scale, 5 items in Social Functioning Scale, and 3 items in School Functioning Scale.

The PedsQL Infant Scales include two age-appropriate versions for ages 1-12 months and 13-24 months, and assess parents' perceptions of their infant's generic Health-Related Quality of Life. The 36-item PedsQL Infant Scales 1-12 months Version encompasses 5 scales: (1) Physical Functioning (6 items), (2) Physical Symptoms (10 items), (3) Emotional Functioning (12 items), (4) Social Functioning (4 items), and (5) Cognitive Functioning (4 items). The 45-item PedsQL Infant Scales 13-24 months Version contains the same 5 scales and the same 36 items as the 1-12 months Version with 9 additional age-appropriate items: (1) Physical Functioning (9 items), (2) Physical Symptoms (10 items), (3) Emotional Functioning (12 items), (4) Social Functioning (5 items), and (5) Cognitive Functioning (9 items). The format, instructions, Likert response scale, and scoring method for the PedsQL Infant Scales are identical to the PedsQL Generic Core Scales for ages 2-18 years.

Each item in every Scale in both parent report and patient report in the above age ranges uses the 4-point rating scale (0=never to 4=almost always). The items of the four Scales are grouped together on the actual questionnaire. The algorithm of Scale Scores ([5](#)) is as follows.

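### The fatigue, pain and quality-of-life questionnaires have an infusion-free baseline, but at Weeks 26 and 52 they may fall in the 12-72 h acute phase reaction window, and nothing controls or adjusts for this

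*Protocol*

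**What the plan says.** **Baseline.** SAP 2.8.13 says of the questionnaires: "These will be evaluated at Screening, Week 26 and Week 52". SAP 2.8 adds: "Baseline for exploratory efficacy variables will be defined as the last non-missing value before the first infusion". The baseline is therefore free of any infusion.

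**On treatment.** Protocol 10.3.5 schedules "Health outcome questionnaires: within 7 days after Week 26 and Week 52 olipudase alfa infusion". The same section has "Pulmonary function testing: within 7 days after Week 26 or Week 52 olipudase alfa infusion" and "Cycle ergometry: within 7 days after Week 26 or Week 52 olipudase alfa infusion"; SAP 2.8.8 repeats the ergometry timing. No minimum interval after the infusion is given for any of them.

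**Reaction window.** Protocol 10.6.1.3.2.2 says that "APR reactions typically occurred within 12-72 hours following an infusion of olipudase alfa and were indicative of an inflammatory response", and then: "Patient AEs associated with the APR included (but are not limited to) pyrexia, nausea, vomiting, fatigue, and pain".

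**Other timing at the same visits.** Protocol 10.3.5 places the physician's global assessment, efficacy biomarkers, lipids and bone biomarkers in the 24 hours before the infusion. Protocol 10.3.1 brings patients back at 24 h and 48 h after the Week 26 and Week 52 infusions, and at 96 h where pharmacokinetic samples require it.

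**Analysis.** SAP 2.11.3 analyses by nominal visit. SAP 2.8.13 summarises scores and change from baseline by age cohort. Neither uses time since infusion.

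**The concern.** A change score is interpretable as a treatment effect only if both measurements are taken under comparable conditions. Here the first is drug-free and the second may fall one to three days after an infusion, when the protocol itself expects some patients to have fatigue and pain. Those are the constructs that two of the questionnaires measure. The first pain item asks about present pain (SAP 2.8.13), so it depends directly on the day of completion.

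At stake is whether a change in fatigue or pain reflects the disease responding to treatment or a passing reaction. Sites that use the 24 h or 48 h return would produce different data from sites that test on Day 6. The study has no comparator (Protocol 6.4) that would cancel such an artefact.

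**Working it through.** The plan gives no figure to reproduce: SAP 1.3 states that there was no power calculation. The check is one of overlapping intervals.

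**1. Overlap of the windows**

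Inputs: allowed period 7 × 24 = 168 h (Protocol 10.3.5); reaction window 12-72 h (Protocol 10.6.1.3.2.2).

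| Time after infusion | Hours | Share of 168 h |
|---|---|---|
| 0-12 h | 12 | 7.1% |
| 12-72 h | 72 − 12 = 60 | 35.7% |
| 72-168 h | 168 − 72 = 96 | 57.1% |

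The allowed period contains the whole reaction window, and most of it lies outside that window.

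**2. Existing return visits**

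With the ±3 h tolerance in Protocol 1.3 and 1.4, the 24 h and 48 h returns fall at 21-27 h and 45-51 h, both inside 12-72 h. The Week 52 pharmacokinetic return is at 96 h ± 3 h in adolescents and at 84-96 h in the younger cohorts (Protocol 1.5), after the window. Week 26 is not a scheduled pharmacokinetic visit, so that later return is not routinely available there.

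**3. How far into maintenance dosing**

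On the schedule in Protocol 8.3.2 without repeats, Weeks 0 to 14 carry 0.03, 0.1, 0.3, 0.3, 0.6, 0.6, 1.0 and 2.0 mg/kg, so the first 3.0 mg/kg infusion is at Week 16.

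- Week 26: (26 − 16)/2 + 1 = 6th infusion at 3.0 mg/kg.
- Week 52: (52 − 16)/2 + 1 = 19th.

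Repeated or missed infusions lower both counts.

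**4. Illustrative size**

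Mean shift = P(assessed in window) × P(reaction) × effect in those affected. The documents give neither of the last two terms. I assume P(reaction) of 0.05 to 0.5 and an effect of 0.5 to 1.0 SD.

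| Timing | Low | High |
|---|---|---|
| Even over 7 days | 0.357 × 0.05 × 0.5 = 0.01 SD | 0.357 × 0.5 × 1.0 = 0.18 SD |
| All in the window | 1 × 0.05 × 0.5 = 0.03 SD | 1 × 0.5 × 1.0 = 0.50 SD |

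**5. Which pre-infusion slot is safe**

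Infusions are every 14 days ± 3 days (Protocol 8.3.3), so two can be 14 − 6 = 8 days apart. A window of 7 days before an infusion could reach back to 8 − 7 = 1 day after the previous one, inside 12-72 h. A window of 24 hours before leaves at least 8 − 1 = 7 days, well beyond 72 h.

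**The case against.** **Attenuation.** The reaction evidence comes from a single-dose study and a dose-escalation study in adults. Protocol 6.4 says that ceramide attenuated with repeat dosing, 6.4.1.1 that rises in acute phase reactants were attenuated under escalation, and 10.6.1.3.2.3 ties IL-6 and IL-8 rises to first administrations at 0.6 to 2.0 mg/kg. Weeks 26 and 52 are normally maintenance infusions. This stands: it lowers the likely size. It does not exclude reactions at those visits. Two of the 5 adults in the Phase 1b study needed a dose reduction or repeat, and SAP 2.6.1.3 still tabulates reactions starting 24 to 72 h after infusion.

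**Tempting stronger readings.** A reader might infer that the assessments lie inside the reaction window and therefore do measure the reaction. The documents support only overlap and risk, since 64% of the allowed time is outside the window. A reader might also extend the point to lung function and cycle ergometry. An effect there is plausible, but no passage says that a reaction changes lung function or workload. A figure of 75% (36 of 48 h) would need testing spread evenly over the first 48 h, which nothing in the documents supports.

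**Limited consequence.** These are exploratory endpoints in a safety study, and a reaction worsens scores, so it would tend to hide a benefit and not create one. This also stands and sets the severity.

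**Unknowns.** The questionnaires' recall period is not stated, and a long recall could capture a reaction under either schedule. Several Protocol 1.2 footnotes were not readable in the copy used, including those on lung function and ergometry. The questionnaire row carries no footnote of its own except at withdrawal.

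**Conclusion.** The point holds for the questionnaires, most clearly for fatigue and pain. Their baseline is infusion-free, their follow-up has no minimum interval after infusion, and the allowed period overlaps the 12-72 h reaction window: 36% of it under even timing, and 100% of assessments if the 24 h or 48 h returns are used. No rule, covariate or sensitivity analysis deals with this.

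The result is a possible bias against the drug plus variation from site scheduling. Its size cannot be derived from the documents. The range of 0.01 to 0.50 SD in the working rests wholly on assumed reaction rates and effects, and attenuation makes the lower part more likely. Severity is low to moderate: a cheap improvement to exploratory endpoints that leaves the primary safety objective untouched.

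**What to change.** **Schedule (Protocol 10.3.5).** Complete the questionnaires within 24 hours before the Week 26 and Week 52 infusions, the slot already used for the physician's global assessment. Do not use a 7-day pre-infusion window, for the reason in step 5 of the working. Lung function and ergometry may stay after the infusion, preferably more than 72 h after it, for example at the 84-96 h pharmacokinetic return at Week 52.

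**Analysis of data already collected (SAP 2.8.13).** Tabulate time since infusion for each questionnaire, by day if clock times were not recorded. Add one supportive change-from-baseline summary that excludes questionnaires completed 12-72 h (or on Days 1-3) after an infusion.

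**Cost.** The pre-infusion visit becomes slightly longer. Moving lung function and ergometry past 72 h may need a separate trip at Week 26, which is why it is only a preference. The supportive summary will rest on a small subset that depends on site scheduling, so it should be read descriptively.
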